### 5.3 Exclusion criteria

Patients eligible for this study must not meet any of the following criteria:

1. Patients with only non-measurable lesions other than bone metastasis as defined above (e.g., pleural effusion, ascites, etc).
2. Patients who have received prior hormonal or any other systemic therapy for metastatic breast cancer.
  - a. Patients may have received prior neoadjuvant or adjuvant endocrine therapy. In the case of neoadjuvant or adjuvant NSAI (letrozole/anastrozole) therapy patients must have completed therapy at least 1 year prior to study enrollment.
3. Previous treatment with mTOR inhibitors.
4. Known hypersensitivity to mTOR inhibitors, e.g., sirolimus (rapamycin).
5. Another malignancy within 5 years prior to enrollment with the exception of adequately treated in-situ carcinoma of the cervix uteri, basal or squamous cell carcinoma or non-melanomatous skin cancer
6. Radiotherapy within four weeks prior to randomization except in case of localized radiotherapy for analgesic purpose of lytic lesions at risk of fracture which can then be completed within two weeks prior to enrollment.
7. Currently receiving hormone replacement therapy, unless discontinued prior to enrollment.
8. History of brain or other CNS metastases.
9. Patients receiving chronic treatment with systemic immunosuppressive agents
10. Bilateral diffuse lymphangitic carcinomatosis.
11. Patients with a known history of HIV seropositivity. Screening for HIV infection at baseline is not required.
12. Active bleeding diathesis.
13. Any severe and/or uncontrolled medical conditions such as:
  - a. Unstable angina pectoris, symptomatic congestive heart failure, myocardial infarction  $\leq$  6 months prior to enrollment, serious uncontrolled cardiac arrhythmia.
  - b. Uncontrolled diabetes as defined by fasting serum glucose  $>1.5 \times \text{ULN}$ .
  - c. Acute and chronic, active infectious disorders (except for Hep B and Hep C positive patients) and nonmalignant medical illness that are uncontrolled or whose control may be jeopardized by the complications of this study therapy
  - d. Impairment of gastrointestinal function or who have gastrointestinal disease that may significantly alter the absorption of study drugs (e.g., ulcerative disease, uncontrolled nausea, vomiting, diarrhea, malabsorption syndrome)
  - e. Active skin, mucosa, ocular or GI disorders of Grade  $>1$
14. Significant symptomatic deterioration of lung function. If clinically indicated, pulmonary function tests including measures of predicted lung volumes, DLco, O2 saturation at rest on room air should be considered to exclude restrictive pulmonary disease, pneumonitis or pulmonary infiltrates.
15. Patients being treated with drugs recognized as being strong inhibitors or inducers of the isoenzyme CYP3A within the last 5 days prior to enrollment (see [Section 6.1.3.1](#))
16. History of non-compliance to medical regimens.

17. Patients unwilling to or unable to comply with the protocol.

## **6 Treatment**

### **6.1 Study treatment**

#### **Definition of terms**

The investigational therapy in the context of this study is everolimus

Study Treatment = Everolimus + Letrozole or Everolimus + Exemestane

Study Drug = Everolimus

Everolimus will be self-administered as a daily dose of 10mg (two 5mg tablets) taken orally continuously from study day 1 until progression of disease, unacceptable toxicity or withdrawal of consent. Everolimus should be taken at the same time every day. Everolimus tablets should be swallowed whole with a glass of water once daily, either consistently with food or consistently without food. Tablets should not be chewed or crushed. Letrozole will be self-administered as a daily dose of 2.5mg continuously from study day 1 until disease progression or any other reason for which the patient may be discontinued (refer to [Section 7.1.5](#)) and should be taken at the same time every day, consistently with or without food. Everolimus and letrozole tablets should be taken together.

During the Core Phase of the study following disease progression on everolimus in combination with letrozole, patients will be offered everolimus in combination with exemestane. Exemestane will be self-administered as a daily dose of 25mg taken orally continuously until disease progression or any other reason for which the patient may be discontinued (refer to [Section 7.1.5](#)) and should be taken at the same time every day. Exemestane should be taken after a meal. Everolimus and exemestane tablets should be taken together.

During the Core Phase and at the onset of symptoms suggestive of stomatitis patients must contact the study site. Upon confirmation of stomatitis at the site, patients in countries where the alcohol-free 0.5mg/5ml dexamethasone oral solution is commercially available will be randomly assigned to take either 0.5mg/5ml dexamethasone mouth rinse or the standard of care used to treat stomatitis at the patient's center. The mouth rinse will be self-administered at a daily dose of 10ml 3 times per day. Patients will be instructed to swish and expectorate the mouth rinse. Patients will also be instructed to fill out the Oral Stomatitis Daily Questionnaire (OSDQ) at home every day until the patient recovers (see [Section 10.5.5.1](#)). During the Extension Phase, standard of care at the patient's site as recommended by the investigator to treat stomatitis will be followed and the OSDQ will not be administered when the patients are in the Extension Phase.

### 6.1.1 Dosing regimen

**Table 6-1 Dose and treatment schedule (first line setting & Extension Phase)**

Study treatments	Pharmaceutical form and route of administration	Dose	Frequency and/or Regimen
Everolimus	Tablet for oral use	10 mg(two 5mg tablets)	Daily (28 day cycles)
Letrozole	Tablet for oral use	2.5mg	Daily (28 day cycles)

**Table 6-2 Dose and treatment schedule (second line setting & Extension Phase)**

Study treatments	Pharmaceutical form and route of administration	Dose	Frequency and/or Regimen
Everolimus	Tablet for oral use	10 mg(two 5mg tablets)	Daily (28 day cycles)
Exemestane	Tablet for oral use	25mg	Daily (28 day cycles)

**Table 6-3 Dose and treatment schedule for oral stomatitis**

Study treatments	Pharmaceutical form and route of administration	Dose	Frequency and/or Regimen
0.5mg/5ml dexamethasone (for patients randomized to dexamethasone treatment)	Oral Solution	10ml	Swish and expectorate 3 times/day

Standard of Care to treat oral stomatitis See [Section 6.2.2.1](#).

### 6.1.2 Treatment duration

#### Core Phase

The study treatment refers to the administration of everolimus in combination with letrozole or exemestane to patients. A treatment cycle consists of 4 weeks (or 28 days). The first day of the open-label study medication begins at Visit 2 (Cycle 1 day 1). The patient must take the first dose of medication at the study center. Patients will receive everolimus 10mg orally daily in combination with letrozole until the occurrence of documented disease progression by RECIST 1.0 criteria or discontinuation due to unacceptable toxicity (with either study treatment) or withdrawal of consent (first line setting). After initial disease progression, patients will be offered everolimus in combination with exemestane according to the treating physician's clinical discretion (see [Section 7.1.3](#)). Patients will be treated in the second line until subsequent disease progression or any other reason for which the patient may be discontinued (refer to [Section 7.1.5](#)).

#### Extension Phase

In the Extension Phase, visits will be every 3 months instead of every 28 days hence patients will be completing approximately 3 treatment cycles between visits. Patients will continue treatment as described in the Core Phase until disease progression or any other reason for which the patient may be discontinued (refer to [Section 7.1.5](#)).

### **6.1.3 Prohibited concomitant therapy**

Patients must be instructed not to take any additional medications (over-the-counter or other products) during the study without prior consultation with the investigator. All medications taken within 28 days of starting study treatment should be reported on the Concomitant Medication eCRF pages.

The following concomitant treatments are not allowed during the study:

- Chronic concomitant bisphosphonate therapy for the prevention of bone metastases are not permitted during the study. Bisphosphonate therapy for the treatment of osteopenia or osteoporosis is permitted during the study. Bisphosphonate or denosumab therapy for the management of bone metastases is recommended as standard of care. Please refer to prescribing information for details of administration. If bisphosphonate or denosumab therapy is initiated after enrollment, the reason for its use must be clearly documented.
- Investigational or commercial anticancer agents, such as chemotherapy, immunotherapy, targeted therapy, biological response modifiers, or endocrine therapy other than exemestane (including steroids) should not be given to patients.
- Hormone replacement therapy, topical estrogens (including any intra-vaginal preparations), megestrol acetate and selective estrogen-receptor modulators (e.g. raloxifene) are prohibited.
- Prolonged systemic corticosteroid treatment, except for topical applications (e.g. rash), inhaled sprays (e.g. obstructive airways diseases), eye drops or local injections (e.g. intraarticular) should not be given. A short duration (<2 weeks) of systemic corticosteroids is allowed (e.g. chronic obstructive pulmonary disease, anti-emetic). Please note, alcohol-free 0.5mg/5ml dexamethasone oral mouth rinse is allowed for patients randomized to receive it at the onset of stomatitis in countries where it is commercially available.
- Hematopoietic growth factors (e.g. erythropoietins, G-CSF and GM-CSF) are not to be administered prophylactically. Use of these should be reserved to cases of severe neutropenia and anemia as per the labeling of these agents.

#### **6.1.3.1 Cytochrome P450 and P-glycoprotein (PgP) inhibitors/inducers/substrates**

Everolimus is metabolized by CYP3A4 in the liver and to some extent in the intestinal wall.

Therefore, the following are recommended:

- Co-administration with strong inhibitors of CYP3A4 (e.g., ketoconazole, itraconazole, ritonavir) or P-glycoprotein (PgP) should be avoided and may cause increased everolimus concentrations.
- Co-administration with moderate CYP3A4 inhibitors (e.g., erythromycin, fluconazole) or PgP inhibitors should be used with caution. If a patient requires co-administration of moderate CYP3A4 inhibitors or PgP inhibitors, reduce the dose of everolimus to half the currently used dose (see [Table 6-9](#) for everolimus dose modifications). Additional dose reductions may be required to manage toxicities. If the inhibitor is discontinued, consider a washout period of at least 2-3 days (average for the most commonly used moderate

[figure not shown]
inhibitors), before the study drug is returned to the dose used prior to initiation of the moderate CYP3A4/PgP inhibitor.

- Co-administration with strong inducers of CYP3A4 should be avoided.
- If a patient requires co-administration of strong CYP3A4 inducers (i.e., phenytoin, carbamazepine, rifampin, rifabutin, phenobarbital, St. John's wort), an increase in the dose of everolimus up to twice the currently used daily dose should be considered, using 5mg increments or less (see [Table 6-9](#) for everolimus dose modifications). This dose adjustment of everolimus is predicted to achieve similar AUC to the range observed without inducers. However, there are no clinical data with this dose adjustment in patients receiving strong CYP3A4 inducers. If the strong inducer is discontinued, consider a washout period of at least 3-5 days (reasonable time for significant enzyme de-induction), before the study drug dose is returned to the dose used prior to initiation of the strong CYP3A4/PgP inducer.

It is to be noted that:

- Local radiotherapy for analgesic purposes or for lytic lesions at risk of fracture may be carried out if required. Whenever possible, these patients should have a tumor assessment of the lesion(s) before they actually receive the radiotherapy. No dose modification of study treatment is needed during radiotherapy.
- Everolimus may affect the response to vaccinations making it less effective. Live vaccines should be avoided while a patient is treated with everolimus.
- Lipid-lowering drugs may be given in case of hyperlipidemia.

Otherwise, the use of other concomitant medication/therapy deemed necessary for the care of the patient is allowed. The investigator should instruct the patient to notify the study site about any new medications she takes after the start of the study drug. All medications (other than study drug) and significant non-drug therapies (including physical therapy and blood transfusions) administered after the patient starts study treatment and for up to 28 days after study drug discontinuation must be listed on the Concomitant medications/Significant Nondrug Therapy After Start of Study Drug eCRF. The first regimen of antineoplastic medication/treatments received after study treatment discontinuation must also be recorded in the antineoplastic treatment eCRF.

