**Strong inducers:**

avasimibe, carbamazepine, enzalutamide, mitotane, phenobarbital, phenytoin, rifabutin, rifampin (rifampicin), St. John's wort (*Hypericum perforatum*)

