**Inducers**

avasimibe, carbamazepine, efavirenz, genistein, phenytoin, quercetin, rifampin, St John's wort

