**PgP Inhibitors and PgP/CYP3A Dual Inhibitors**

PgP Inhibitors

alogliptin, canagliflozin, cremophor RH40, curcumin, ketoconazole, lapatinib, lopinavir/ritonavir, mirabegron, propafenone, simeprevir, valspar, vandetanib, voclosporin

PgP/CYP3A Dual Inhibitors

amiodarone, azithromycin, captoril, carvedilol, clarithromycin, conivaptan, diltiazem, dronedarone, elacridar, erythromycin, felodipine, fluvoxamine, ginkgo (*Ginkgo biloba*), indinavir, indinavir/ritonavir, itraconazole, mibepradil, milk thistle (*Silybum marianum*), neflifavir, nifedipine, nitrendipine, paroxetine, quercetin, quinidine, ranolazine, rifampin, ritonavir, saquinavir/ritonavir, *Schisandra chinensis*, St John's wort (*Hypericum perforatum*), talinolol, telaprevir, telmisartan, ticagrelor, tipranavir/ritonavir, tolvaptan, verapamil

Reference: Internal Clinical Pharmacology Drug-drug interaction (DDI) memo, updated April-2015 which summarizes DDI data from three sources including the FDA's "Guidance for Industry, Drug Interaction Studies", the University of Washington's Drug Interaction Database, and Indiana University School of Medicine's Drug Interaction Table.

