#### **6.2.2.10 Permitted study drug adjustments**

For patients who may require dose adjustments because of concomitant medication, please refer to [Section 6.1.3](#). For patients who are unable to tolerate the protocol-specified dosing schedule, dose adjustments are permitted in order to allow the patient to continue study drug. The following guidelines should be followed. These changes must be recorded on the Dosage Administration Record eCRF. If treatment is interrupted due to toxicity, study drug should not be resumed until recovery to Grade  $\leq 1$ . Study drug can then be reintroduced at the initial dose or a lower dose level depending on the toxicity type and Grade (see [Table 6-9](#), [Table 6-10](#), [Table 6-11](#)).

These changes must be recorded on the Dosage Administration Record eCRF.

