**Table 6-9 Dose reduction steps for everolimus**

Dose reduction*			
	Starting dose level	Dose level – 1	Dose level - 2
Everolimus	10 mg daily	5 mg daily	5 mg every other day**

\*Dose reduction should be based on the worst toxicity demonstrated at the last dose received.  
\*\*Dose reduction below 5 mg every other day is not allowed. Treatment must be discontinued.

Management of severe or intolerable adverse drug reactions (ADRs) may require temporary dose interruption (with or without dose reduction) or discontinuation of everolimus therapy. If dose reduction is required, the suggested dose is approximately 50% lower than the daily dose

previously administered. For dose reductions below the lowest available tablet strength, alternate day dosing should be considered.

**Table 6-10** and **Table 6-11** summarize the recommendations for dose interruption, reduction, or discontinuation of everolimus in the management of ADRs. General management recommendations are also provided as applicable. Clinical judgment of the treating physician should guide the management plan of each patient based on individual benefit/risk assessment.

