**Table 6-11 Dosing guidelines for study drug-related hematologic toxicities**

Adverse event	Severity 	Everolimus Dose Adjustment
Platelet count decreased (Thrombocytopenia)	Grade 1 (<LLN-75.0x10  /L)	No dose adjustment required.
	Grade 2 (<75.0-50.0x10  /L)	Temporary dose interruption until recovery to Grade $\leq$ 1. Re-initiate everolimus at the same dose.
	Grade 3 (<50.0-25.0x10  /L)	Temporary dose interruption until recovery to Grade $\leq$ 1. Re-initiate everolimus at a lower dose.
	Grade 4 (<25.0x10  /L)	Temporary dose interruption until recovery to Grade $\leq$ 1. Re-initiate everolimus at a lower dose.
Neutrophil count decreased (Neutropenia)	Grade 1 (<LLN-1.5x10  /L)	No dose adjustment required.
	Grade 2 (<1.5-1.0x10  /L)	No dose adjustment required.
	Grade 3 (<1.0-0.5x10  /L)	Temporary dose interruption until recovery to Grade $\leq$ 2 (ANC $\geq$ 1.0x10  /L). Re-initiate everolimus at the same dose.
	Grade 4 (<0.5x10  /L)	Temporary dose interruption until recovery to Grade $\leq$ 2 (ANC $\geq$ 1.0x10  /L). Re-initiate everolimus at a lower dose.
Febrile neutropenia	Grade 3 (ANC <1.0x10  /L with single temperature $>$ 38.3° C (101°F) or sustained temperature $\geq$ 38°C (100.4°F) for $>$ 1h)	Temporary dose interruption until recovery to Grade $\leq$ 2 (ANC $\geq$ 1.25x10  /L) and no fever. Re-initiate everolimus at a lower dose.
	Grade 4 (Life-threatening consequences; urgent intervention indicated)	Discontinue everolimus.
Any hematologic toxicity requiring study drug interruption for $>$ 28 days		Discontinue everolimus.

 Grading based on National Cancer Institute (NCI) Common Terminology Criteria for Adverse Events (CTCAE) v4.03

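### Three everolimus dose-change rules contradict each other: rifampin and St John's wort fall under both the halving and the increase rule, and the neutropenia restart threshold and the 28-day rule differ between text and tables

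*Protocol*

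**What the plan says.** **Co-medication (Section 6.1.3.1, Tables 6-4, 6-5 and 6-9).**

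- For inhibitors, the text gives an instruction: "If a patient requires co-administration of moderate CYP3A4 inhibitors or PgP inhibitors, reduce the dose of everolimus to half the currently used dose".
- For inducers that the patient requires, it speaks of "strong CYP3A4 inducers (i.e., phenytoin, carbamazepine, rifampin, rifabutin, phenobarbital, St. John's wort), an increase in the dose of everolimus up to twice" the current daily dose, as something to consider. It also says that such drugs should be avoided.
- Table 6-4 puts both drugs among the strong inducers: "phenobarbital, phenytoin, rifabutin, rifampin (rifampicin), St. John's wort".
- Table 6-5 lists them as PgP inducers: "phenytoin, quercetin, rifampin, St John's wort".
- Table 6-5 lists them again under PgP/CYP3A dual inhibitors: "ranolazine, rifampin, ritonavir, saquinavir/ritonavir, *Schisandra chinensis*, St John's wort".
- Both dose rules send the reader to Table 6-9, whose title is "Dose reduction steps for everolimus".

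**Restart after neutropenia (Section 6.2.2.10, Table 6-11).**

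- The general text, for any interruption due to toxicity, says: "study drug should not be resumed until recovery to Grade $\leq 1".
- The Grade 3 and Grade 4 neutropenia rows of Table 6-11 say: "Temporary dose interruption until recovery to Grade $\leq$ 2 (ANC $\geq$ 1.0x10" (units of 10^9/L).
- The Grade 3 febrile neutropenia row also restarts at Grade 2 or better, but equates that with ANC of at least 1.25 and requires absence of fever.

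**Length of interruption (Section 6.2.2.9, Tables 6-7 and 6-11).**

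- Section 6.2.2.9 requires the patient to leave the study at a delay of 28 days or more.
- Table 6-7 restarts study drug one dose lower, if one is available, when hepatitis B reactivation resolves within 28 days inclusive. It stops study drug only beyond that.
- The last row of Table 6-11 discontinues everolimus for a hematologic interruption longer than 28 days.

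**The concern.** A site following the written rules can change the dose in opposite directions for the same co-medication, restart after neutropenia at different neutrophil counts, or handle day 28 in different ways. That is first a patient-safety matter.

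It also affects the data. Section 10.3.1 summarizes dose intensity, dose changes and their reasons in both phases, and these will be less uniform if sites apply different rules.

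The rules are still in use. Amendment 5 continues treatment for up to three years, and at the June 2016 cut-off 64 + 19 = 83 patients were on treatment. In the Extension Phase, safety laboratory tests are done only as clinically indicated (Section 7.1.4) and concomitant medications are not collected (Section 10.3.2). Sites then depend more on the written rules, and a co-medication behind a dose change may not be traceable.

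**Working it through.** The protocol states no figure to reproduce here. The check sets the current rules side by side and works out where they part.

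**1. Overlap of drug classes**

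- Strong inducers named in Section 6.1.3.1: phenytoin, carbamazepine, rifampin, rifabutin, phenobarbital, St John's wort = 6.
- Strong inducers in Table 6-4: these six plus avasimibe, enzalutamide and mitotane = 9.
- Of these, the ones also in the inhibitor lists of Table 6-5: rifampin and St John's wort = 2, that is 2 of 6 and 2 of 9.
- A dual PgP/CYP3A inhibitor is by its name a PgP inhibitor, so it meets the trigger of the halving rule.
- At the 10 mg starting dose, halving gives 10 x 0.5 = 5 mg. The increase rule gives at most 10 x 2 = 20 mg. The directions are opposite, and at the upper bound the ratio is 20 / 5 = 4.
- Table 6-9 holds 10 mg daily, 5 mg daily and 5 mg every other day. Levels above 10 mg: none. The reference works for halving from 10 mg but offers no step for an increase.

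**2. Restart threshold**

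Grade limits for neutropenia in Table 6-11 (x10^9/L): the lower limit of Grade 1 is 1.5, and Grade 2 runs from 1.0 to below 1.5. Grade 1 or better therefore means ANC of at least 1.5.

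| ANC at recovery | Neutropenia rows | Febrile neutropenia row (no fever) | Section 6.2.2.10 |
|---|---|---|---|
| 1.0 to below 1.25 | restart | Grade 2 by the table's own limits, but below this row's ANC figure | no restart |
| 1.25 to below 1.5 | restart | restart | no restart |
| 1.5 or more | restart | restart | restart |

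The text and the neutropenia rows conflict from 1.0 to below 1.5. The text and the febrile neutropenia row conflict from 1.25 to below 1.5. Table 6-11 also contradicts itself from 1.0 to below 1.25, because it equates Grade 2 or better with two different counts.

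**3. The 28-day rule**

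| Length | Section 6.2.2.9 | Table 6-7 | Table 6-11, last row |
|---|---|---|---|
| under 28 days | continue | restart | no stop |
| exactly 28 days | off the study | restart | no stop |
| over 28 days | off the study | off study drug | off everolimus |

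The timing conflict is confined to day 28. The consequence differs for every longer delay as well: leaving the study is not the same as stopping the drug. Sections 4.1, 7.1.6.2 and 7.2.1 keep patients who stop treatment under survival follow-up and, in the Core Phase, tumor assessment.

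**The case against.** **Co-medication.** The text names both drugs under the increase rule, and nothing names them under the halving rule. They appear only under the dual-inhibitor subheading of Table 6-5. That list also holds drugs such as clarithromycin and itraconazole, which Table 6-4 calls strong inhibitors and the text says to avoid. The tables merge three outside sources, so double listings are common: ritonavir, aprepitant and cimetidine each appear in more than one class. The increase is discretionary, for drugs to be avoided anyway, and the text itself gives increments for it. This limits how often the conflict will arise and makes 20 mg an upper bound. It does not remove the conflict: both rules are written for a patient who requires the drug, the halving rule is the firmer of the two, and no precedence is stated.

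**Restart threshold.** A toxicity-specific row with an ANC figure could be read as overriding the general sentence, and the text accompanying Table 6-9 leaves room for clinical judgment. But Section 6.2.2.10 uses the tables to choose the dose after recovery to Grade 1 or better, and nowhere calls them exceptions. That reading also leaves the two ANC figures for the same grade in Table 6-11.

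**28 days.** Table 6-7 times resolution while Section 6.2.2.9 times dose delay, so the clocks differ slightly, and the glossary allows a withdrawn patient to be followed for progression or survival. Survival follow-up ended 24 months after 17 December 2014, before Amendment 5 of 14 February 2017. Extension Phase patients have no protocol imaging and no survival follow-up. So the mismatch over leaving the study matters for the Core Phase only, and any alignment must carry that limit.

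**Conclusion.** The concern holds on all three counts, in current text rather than in the amendment log.

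- Two drugs, 2 of the 6 strong inducers named in Section 6.1.3.1, meet two rules of opposite direction. This rests on reading a dual inhibitor as a PgP inhibitor, as its name says.
- The restart rules disagree over ANC 1.0 to below 1.5 x10^9/L after neutropenia and 1.25 to below 1.5 after febrile neutropenia. This rests on applying Table 6-11's own neutropenia grade limits.
- The 28-day rules disagree on day 28 itself, and on leaving the study versus stopping the drug for longer delays.

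The documents do not show how often any of these situations arises. No bias in PFS or OS is claimed, because continued follow-up after stopping treatment is already required elsewhere. The matter should be corrected because contradictory safety instructions remain in force and the correction is cheap. No view is taken here on which dose or rule is right.

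**What to change.** The sponsor should reconcile:

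1. Section 6.1.3.1 with Tables 6-4 and 6-5 for rifampin and St John's wort, together with the reference to Table 6-9 for dose increases.
2. Section 6.2.2.10 with the neutropenia and febrile neutropenia rows of Table 6-11, including the two ANC figures given for Grade 2 or better.
3. Section 6.2.2.9 with Tables 6-7 and 6-11 on the 28-day limit. The wording on leaving the study should be aligned with the follow-up in Sections 4.1, 7.1.6.2 and 7.2.1, keeping their Core Phase limit.

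Each situation should carry one instruction, or the protocol should state whether table or text prevails. In the same pass, correct the listing of grapefruit juice in Table 6-4 as both a strong and a moderate inhibitor.

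Cost: wording and table corrections in the next amendment and a short site notice. No extra procedures, visits or data are needed.
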